Given the complexity of the correlation structure present in periodontal PD data, the variability in the number of probing sites a given patient participant presents with, and the variability of the correlation in sites depending on which teeth are present, a custom simulation was conducted to further explore the power of this design. In the simulation, patient participants are added to the study with a random number of existing teeth ranging from twenty to twenty-eight, with anterior teeth being added with greater probability than posterior teeth. In order to assign baseline PDs, a correlation structure was constructed in which sites on the same teeth are more highly correlated with each other and sites on different teeth are assigned a correlation based on the distance between them. Simulated baseline PDs are then added with an average depth of 4.5 mm. Similarly changes from baseline were simulated using a similar correlation structure with an average change of 0.3 mm being assumed for the placebo group, a 0.5mm in the AMXM group), and a standard deviation of 1 mm for both groups. This difference of 0.2 mm was chosen as it was determined to be a small but clinically meaningful difference. This synthetic data was then analyzed using the hierarchical model described in section 12.4. The simulation suggested that a sample size of N=220 per arm would be sufficient to achieve 90% power for detecting an average reduction of PD=0.2 mm. Sensitivity analyses were conducted which suggested that by choosing to design the study to a relatively high power of 90%, the design is likely to have adequate power of >80% even if the observed correlation in the study, observed average number of teeth remaining, or the positioning of remaining teeth deviate from that which was included in our initial simulation by a moderate amount. After accounting for a potential dropout rate of 20% and to distribute an even number of patient participants across thirty-four practitioners, the final total sample size would be N=544 or 272 per arm.

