12.4 Final Analysis Plan

Analysis Population: All analyses will be intent-to-treat, i.e., all participants who provide data at baseline will retain their original assignment regardless of the treatment received. All statistical tests will be evaluated using a two-tailed alpha level of .05 and will express precision using 95% confidence intervals.

Center Effects: The Primary analysis will account for variation between centers using a mixed effects model. The empirical Bayes estimate of center effects resulting from this model will be analyzed to assess the degree of heterogeneity between centers by assessing the magnitude of the variance of the random effects. This assessment will consist of a formal statistical test to determine if the variance of the random effect is greater than zero as well as an assessment of its estimated magnitude. If a clinically meaningful amount of variability between centers is detected, exploratory analyses will be conducted to attempt to identify covariates related to center effects including

geographic information, demographic information, and disease-related information. If these analyses identify meaningful subgroups among the centers, subgroups of sites will be created based on the potential for differential effectiveness. These subgroup analyses will be considered secondary and will be conducted in a manner identical to the primary analysis provided that the subgroups are of sufficient size to merit such an analysis. The specific data related to the characteristics of these subgroups, should they prove to exist, will be reported separately.

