Primary Outcome Analysis: We will test the primary study hypothesis, which posits the AMXM intervention to be more effective than placebo in reducing periodontal probing depths, using a hierarchical linear model (HLM; aka mixed models, random coefficients regression). This analysis will account for the correlation between longitudinal observations within tooth site, within participants, and by practitioner, each of which can be represented within the model by a random intercept. The primary outcome measure, PD in mm, is effectively continuous, within a fixed range being necessarily positive and bounded above by the anatomy of the tooth in question. The model will include the fixed effect of time by using two dummy indicators representing re-evaluation at 6 weeks and final study visit at 12 months. The model will also include a binary indicator for arm (AMXM vs placebo) and an interaction between the indicators for time and study arm. Significance of either interaction term will represent a difference between the treatment and control arm at that timepoint, with the 6-week time representing efficacy and the 12-month time representing long-term efficacy/durability. No transformation of these variables is likely to be necessary.

It is not presently anticipated that boundary value problems or deviations in the residual distribution of the primary outcome will negatively impact the proposed analysis' operating characteristics due to the large size of the study. However, sensitivity of the analysis to these factors will be assessed using residual plots. In addition, potential site effects and the impact of any overly influential sites will be investigated by assessing the cluster-bootstrap stability of the analysis. Resampling analysis will be conducted stratified by person and site. The analysis will be conducted within each replication and the variability will be assessed in terms of statistical significance, clinically meaningful effect size, and the distribution of observed treatment effects. Any deviations impacting performance will be mitigated by modification of the primary analysis potentially to an approach utilizing the Huber-White sandwich estimator for the variance.

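### As described, the primary model's random intercepts cancel from the arm-by-visit contrast, so its standard error treats all site changes in a mouth as independent

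*Protocol*

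**What the plan says.** The primary outcome is site-level probing depth over the full mouth at baseline, 6 weeks and 12 months. Protocol section 12.4 (Primary Outcome Analysis) proposes a hierarchical linear model for correlation within tooth site, "within participants, and by practitioner, each of which can be represented within the model by a random intercept". Visits enter as a "fixed effect of time by using two dummy indicators representing re-evaluation at 6 weeks and final study visit at 12 months", so baseline is an outcome row and the reference. The test is the arm-by-visit interaction: "Significance of either interaction term will represent a difference between the treatment and control arm at that timepoint". Section 4.2 gives the same levels (visits in sites in participants, plus a practitioner intercept), and the secondary analyses in section 12.4 repeat them for site, patient and provider with time fixed. No participant-by-visit effect is stated anywhere.

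Section 12.2 describes the power simulation. Baseline depths are correlated within and between teeth. "Similarly changes from baseline were simulated using a similar correlation structure", with a mean change of 0.3 mm on placebo, 0.5 mm on AMXM and an SD of 1 mm. "This synthetic data was then analyzed using the hierarchical model described in section 12.4", and 220 per arm is reported to give 90% power for 0.2 mm.

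As safeguards, section 12.4 lists residual plots and a cluster-bootstrap stability check ("Resampling analysis will be conducted stratified by person and site"). If performance is affected, the primary analysis is to be modified, potentially to a Huber-White sandwich variance.

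**The concern.** A participant intercept captures the fact that some people have deeper pockets at every visit. It does not capture the fact that some people respond better than others, so that all their sites improve together. The arm-by-visit interaction depends on that second kind of variation. The Protocol expects it: section 12.2 simulates correlated changes, and section 2.1 describes response to treatment as highly variable between individuals.

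If the model omits this variation, the number of sites, rather than the number of participants, sets the precision of the treatment effect. The primary p-value and confidence interval would then be too optimistic, and the sample size would rest on a model different from the one described.

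**Working it through.** **Inputs.** Two-sided alpha 0.05 (section 12.4: "All statistical tests will be evaluated using a two-tailed alpha level of .05"). From section 12.2: n = 220 per arm, effect 0.2 mm, SD of site-level change 1 mm, 90% power, 20% dropout, 20 to 28 teeth. Six sites per tooth (section 7.1), so m = 120 to 168 sites; 24 teeth, hence m = 144, is an assumed midpoint. The average correlation ρ between site changes within a participant is not given, so it is varied.

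**1. The plan's own figure.** 220/(1 − 0.20) = 275 per arm, or 550 in total. The stated 544 is 34 × 16 and leaves 544 × 0.80/2 = 217.6 per arm, which is close enough. The 220 itself cannot be recomputed without ρ, but it can be inverted for a test with a valid standard error:
- Required SE = 0.2/(1.96 + 1.2816) = 0.0617 mm.
- SD of participant-mean change = 0.0617 × √(220/2) = 0.647 mm.
- ρ = (0.647² − 1/144)/(1 − 1/144) ≈ 0.41, and essentially the same for m = 120 or 168.

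**2. What the stated model estimates.** Write depth as fixed part + practitioner + participant + site + residual. In follow-up minus baseline the three intercepts drop out, leaving a difference of two residuals that the model takes as independent over sites. With balanced data the interaction is the between-arm difference in mean change, and its model standard error is

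SE(model) = √(2·SD²/(n·m)) = √(2/(220 × 144)) = 0.0079 mm.

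Any participant-by-visit variance goes into the residual, so this value is the same at every ρ. In a small test case the closed form agreed with a fitted mixed model with participant and site intercepts (0.0802 from both).

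**3. What the standard error should be.** With DEFF = 1 + (m − 1)ρ, the true SE is 0.0079 × √DEFF, and the actual two-sided error is 2[1 − Φ(1.96/√DEFF)].

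| ρ (assumed) | DEFF | True SE (mm) | Type I error per visit, m = 144 | Range, m = 120 to 168 |
|---|---|---|---|---|
| 0.01 | 2.43 | 0.012 | 21% | 18.5% to 23.0% |
| 0.05 | 8.15 | 0.023 | 49% | 45.7% to 52.2% |
| 0.10 | 15.30 | 0.031 | 62% | 58.5% to 64.1% |
| 0.41 | 59.63 | 0.061 | 80% | 78.1% to 81.4% |

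**4. Simulation under no effect** (220 per arm, 144 sites, three visits, 300 runs). The 6-week term rejected in 22%, 45%, 63% and 85% of runs at ρ = 0.01, 0.05, 0.10 and 0.41. Either term rejected in 40%, 68%, 84% and 96%; these figures also include ordinary two-test multiplicity and assume participant effects independent across visits. A test on participant-mean changes, applied to the same data, rejected in 4% to 6%.

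**5. Power.** Power of the stated test is Φ[(0.2 − 1.96 × 0.0079)/true SE]. It is lowest at ρ = 1, where the true SE is 0.0953 mm: Φ(1.93) ≈ 97%. At ρ = 0.41 it is 99.9%. With independent changes about 4 participants per arm would suffice: 2 × (3.2416/0.2)²/144 ≈ 3.6. A valid participant-level test at n = 220 and ρ = 0.41 gives 90.3%.

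**The case against.** The best defence is that intercepts only is not firmly fixed. The text says the levels can be represented by random intercepts, it gives random coefficients regression as another name for the model class, and the moderator paragraph has participant-level terms predicting every level 1 term. A statistical analysis plan that is not shown may state the covariance. Section 3.1 speaks of follow-up depth adjusted for baseline; in a model of that type a participant intercept would largely handle clustering for an arm effect. The power result points the same way: if intercepts only cannot give 90%, perhaps the simulation used something else. These points limit how far the criticism reaches, but none of them states a participant-by-visit effect. Section 12.4 keeps baseline as an outcome and tests the interaction. The power argument also leaves sections 12.2 and 12.4 in need of reconciliation.

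The safeguards deserve a fair reading. A cluster bootstrap normally resamples clusters, section 12.4 applies it to model misspecification as well, and it says that deviations will be mitigated. A reader might infer from "Resampling analysis will be conducted stratified by person and site" that every person is held fixed, so that between-person variation cannot appear. The wording is ambiguous and does not establish that. It does establish that there is no trigger and no named cluster level, and that the remedy would be chosen after results are seen.

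Two further inferences go too far. A tooth-level term is not required: with tooth-correlated changes under no effect, a participant-level test that ignored tooth rejected in 4.4% of runs. The centre step ("to assess the degree of heterogeneity between centers by assessing the magnitude of the variance of the random effects") looks at differences in mean depth rather than in treatment effect, but it is exploratory, it leads to subgroups only after covariates are examined, and it leaves the primary p-value untouched.

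**Conclusion.** The concern holds for the model as described. Its interaction standard error of about 0.008 mm ignores participant-level variation in change that the Protocol itself assumes, and even an average correlation of 0.01 raises the nominal 5% to about 21%. The stated 90% power does not belong to that model on the stated inputs; it fits a valid participant-level test if the average correlation is about 0.41.

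Every error rate depends on a correlation that the Protocol does not give, on about 144 sites, and on balanced data. The 0.41 is itself derived by assuming a valid standard error, so the 80% beside it shows what the stated model would do at that correlation and is not a forecast.

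A reader might infer that an ineffective drug would usually be declared effective. The figures do not support this: the test is two-sided, so about half of the false rejections favour placebo. Per-visit false claims of benefit are about 10%, 25%, 31% and 40% across the table. Nor do the 144-site figures carry over to the secondary outcomes. CAL and BoP are half-mouth (about 72 sites), residual disease is analysed by tooth, and exact cancellation does not apply to logistic models. Those models share the structural gap, but its size has not been worked out here.

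**What to change.** - In section 12.4, prespecify as primary either participant-level random effects for the two visit indicators (a participant-by-visit effect) or participant-clustered robust standard errors. One of the two is enough; a tooth-by-visit term is optional.
- State that the bootstrap resamples whole participants.
- Confirm which model the section 12.2 simulation used. Rerun it with the respecified model, state the assumed correlation, and report type I error as well as power.
- Apply the same participant-level handling to the site-level CAL, BoP and residual-disease models.

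The cost is Protocol wording, some recoding and a rerun of an existing simulation. Confidence intervals will be wider, and correct. No new data are needed, and 220 per arm remains adequate if the average correlation is about 0.41 or lower.

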3 OBJECTIVES AND OUTCOME MEASURES

3.1 Primary

Objective	Brief Description/Justification of Outcome Measure	Outcome Measured By	Time Frame
Assess the effectiveness of SRP plus AMXM compared to SRP with placebo in periodontitis individuals at baseline, reevaluation (6 weeks), and final visit (12 months) following intervention.	The primary outcome of treatment effectiveness will be assessed by full-mouth probing depth (PD) at 6 weeks to 12 months post-intervention adjusted for baseline PD. These are considered universal, standard assessments used to determine periodontal status (Tonetti et al. 2018). A double-blinded patient participant-randomized design is used to assign patient participants to SRP plus AMXM versus SRP plus placebo prior to treatment.	Outcome: Probing Depth (PD) in millimeters. Full- mouth PD measurements (excluding 3rd molars) will be obtained utilizing a UNC 15mm periodontal probe. Level of analysis: site Outcome Type: continuous	Baseline, Re- evaluation (6 weeks), and Final study visit (12 months) after intervention.

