3.2 Secondary

Objective	Brief Description/ Justification of Outcome Measure	Outcome Measured By	Time Frame
Assess changes in periodontal tissue attachment comparing SRP plus AMXM to SRP plus placebo in periodontitis individuals at baseline, reevaluation (6 weeks), and final visit (12 months) following intervention.	This secondary objective will be assessed by clinical attachment level (CAL) changes from baseline to 6 weeks to 12 months post-intervention, adjusting for baseline CAL. CAL is a disease-related characteristic. The assessment will employ a validated diagonal protocol (Vettore MV et al. 2007) including one maxillary and one mandibular quadrant to evaluate CAL.	Outcome: Half-mouth CAL in millimeters (excluding 3rd molars) will be obtained utilizing a UNC 15mm periodontal probe to measure base of pocket to cementoenamel junction (CEJ). Level of analysis: site Outcome Type: continuous	Baseline, Re- evaluation (6 weeks), and Final study visit (12 months) after intervention.

Objective	Brief Description/ Justification of Outcome Measure	Outcome Measured By	Time Frame
Assess changes in the probability of bleeding on probing (BoP) at a given site comparing SRP plus AMXM to SRP with placebo in periodontitis individuals at baseline, reevaluation (6 weeks), and final visit (12 months) following intervention.	This secondary objective will assess changes in the probability of observing BoP, a common surrogate for gingival inflammation, at 6 weeks to 12 months post intervention, adjusting for baseline BoP. The assessment will utilize a diagonal protocol (one maxillary and one mandibular quadrant) to evaluate BoP.	Outcome: BoP is assessed in conjunction with probing depths using a UNC 15mm periodontal probe and is recorded as a binary outcome per site, i.e., is the site bleeding? Yes/No Level of analysis: site Outcome Type: binary (no/yes)	Baseline, Re- evaluation (6 weeks), and Final study visit (12 months) after intervention.

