Assess the reduction in diseased sites comparing SRP plus AMXM to SRP with placebo in periodontitis individuals at baseline, reevaluation (6 weeks), and final visit (12 months) following intervention.	Reduction in diseased sites is a calculated variable from PD. We will assess the probability a site is observed with residual PD≥ 5 mm at 6 weeks to 12 months post-intervention, adjusting for its baseline PD. This is a common outcome related to the primary outcome (change in PD), which better reflects further treatment needs.	Outcome: PD≥ 5mm; The maximum probing depth per tooth will be recorded as ≥5 mm (yes/no). Level of analysis: site Outcome Type: binary (no/yes)	Baseline, Re- evaluation (6 weeks), and Final study visit (12 months) after intervention.
Assess disease remission between arms of SRP plus AMXM compared to SRP with placebo in periodontitis individuals at baseline, reevaluation (6 weeks), and final visit (12 months) following intervention.	Disease remission is defined as the number of study patient participants who have ≤4 sites with PD≥5mm (Feres et al. 2020). This variable is calculated from PD≥ 5mm.	Outcome: Number of patient participants with ≤4 sites with PD≥ 5mm; Patient participants will be considered 'in remission' if they display ≤4 sites with PD≥ 5mm; This is a dichotomization from the summation of PD≥ 5mm within person.	Re-evaluation (6 weeks), and Final study visit (12 months) after intervention.
		Level of analysis: person Outcome Type: binary (no/yes)	

Objective	Brief Description/ Justification of Outcome Measure	Outcome Measured By	Time Frame
Evaluate patient- reported changes in oral health-related quality of life comparing SRP plus AMXM to SRP with placebo in periodontitis individuals at baseline, re- evaluation (6 weeks), and final visit (12 months) following intervention.	To evaluate oral health-related quality of life, the Oral Health Impact Profile (OHIP-5) will be utilized. The OHIP-5 is an abbreviated patient-reported outcome measure (PROM) that gauges oral-health related quality of life status (John 2022). This provides insight on the patient participant's perception of their individual oral health status.	Outcome: OHIP-5 sum score based upon self-reported responses. Level of analysis: person Outcome Type: continuous	Baseline, Re- evaluation (6 weeks), and Final study visit (12 months) after intervention.

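### Section 3 defines four outcomes as adjusted for baseline, but the models fixed in 12.4 contain no baseline outcome covariate and test differences in change

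*Protocol*

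**What the plan says.** **Section 3.** The primary outcome (3.1) is "full-mouth probing depth (PD) at 6 weeks to 12 months post-intervention adjusted for baseline PD". In 3.2, CAL is assessed by "changes from baseline to 6 weeks to 12 months post-intervention, adjusting for baseline CAL", BoP "at 6 weeks to 12 months post intervention, adjusting for baseline BoP", and residual PD of 5 mm or more "at 6 weeks to 12 months post-intervention, adjusting for its baseline PD". For OHIP-5 the entry is "OHIP-5 sum score based upon self-reported responses", with no baseline adjustment mentioned. Remission has none either.

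**Section 12.4, Primary Outcome Analysis.** The fixed effects are listed. Time enters through "two dummy indicators representing re-evaluation at 6 weeks and final study visit at 12 months". Then: "The model will also include a binary indicator for arm (AMXM vs placebo) and an interaction between the indicators for time and study arm". The test is on the interactions: "Significance of either interaction term will represent a difference between the treatment and control arm at that timepoint". Correlation is handled by random intercepts for tooth site, participant and practitioner.

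**Section 12.4, Analysis of Secondary Measures.** CAL and OHIP-5 use the same framework. BoP and residual disease use a logit link with the same terms.

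**Section 12.2.** The 90% power at 220 per arm came from a simulation analysed with the 12.4 model.

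**The concern.** Two visit indicators plus an intercept imply three outcome times, so baseline is an outcome row. With only two follow-up visits, an arm term and two arm-by-visit terms could not all be estimated. The paragraph on remission points the same way: that model is non-longitudinal because the outcome does not vary at baseline, so the others do include baseline. The arm main effect is then a freely estimated baseline difference between arms, and each interaction subtracts that difference in full.

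This is not adjustment for baseline in the sense of Section 3. Two things are at stake. First, when the arms differ by chance at baseline, the two analyses give different numbers from the same data, and the protocol supports either. Second, randomisation makes the expected baseline difference zero, so subtracting the observed difference in full can add noise that regression adjustment would avoid.

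**Working it through.** **1. The passages side by side**

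| Outcome | Section 3 | Section 12.4 tests |
|---|---|---|
| PD | follow-up PD, adjusted for baseline PD | difference in mean change |
| CAL | change, also adjusted for baseline CAL | difference in mean change |
| BoP | adjusted for baseline BoP | difference in log-odds change |
| PD ≥5 mm | adjusted for the site's baseline PD | difference in log-odds change |
| OHIP-5 | no adjustment stated | difference in mean change |

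For PD and CAL with complete data, the arm-by-visit coefficient in a random-intercept model equals the difference between arms in mean change. The conflict is plainest for PD ≥5 mm: the continuous baseline PD that 3.2 names is in no model, since the baseline row there is the dichotomised value.

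**2. The plan's own figure**

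Inputs from 12.2 and 12.4: difference 0.2 mm, SD of change 1 mm, two-sided alpha 0.05, power 90%, 220 per arm. One independent value per participant would need 2 × (1.960 + 1.282)² × 1² / 0.2², about 526 per arm. The 220 comes from a custom simulation whose site correlations are not given, so it cannot be reproduced in closed form. Solving backwards, the participant-level SD of change that makes 220 correct is 0.2 × √(220/2) / 3.242 = 0.647 mm. The standard error (SE) of the difference in change is then 0.647 × √(2/220) = 0.0617.

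**3. Variance with and without adjustment**

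Let s0 be the SD of participant-mean baseline and b the slope of follow-up on baseline.

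- Var(change) − Var(adjusted) = (1 − b)² × s0². This is never negative, and is zero when b = 1, that is, when change is unrelated to baseline.
- With equal variances at both times b = r, and the ratio adjusted/change is (1 − r²) / [2(1 − r)] = (1 + r)/2.

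The correlation r is an assumption; the protocol states none. Holding the SD of change at 0.647:

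| Assumed r | Variance ratio | n per arm for 90% | Power at 220 per arm | Excess SE of raw change |
|---|---|---|---|---|
| 0.5 | 0.75 | 165 | 96.3% | 15.5% |
| 0.6 | 0.80 | 176 | 95.2% | 11.8% |
| 0.7 | 0.85 | 187 | 94.0% | 8.5% |
| 0.8 | 0.90 | 198 | 92.7% | 5.4% |
| b = 1 | 1.00 | 220 | 90.0% | 0% |

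A simulation on participant means (4,000 replicates, 220 per arm) agrees. Both analyses average −0.20 mm. At r = 0.6, power is 90.2% for change and 95.1% adjusted. At b = 1 it is 89.4% and 89.5%.

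**4. Would removing the arm main effect be enough?**

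Assume 144 sites per participant and site residual variance 0.5 (neither is in the protocol). With random intercepts only, the model implies a correlation near 1 between a participant's mean values at different visits, so it subtracts baseline almost in full either way. The SEs below are true sampling SEs at r = 0.6, not the ones the fitted model would report.

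| Covariance | Arm effect free at baseline | Common baseline mean |
|---|---|---|
| Random intercepts only | 0.0617 | 0.0615 |
| Participant-by-visit covariance | 0.0617 | 0.0552 |

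**The case against.** The best defence is that change is what the protocol means. The Protocol Summary, 4.2 and 12.2 all describe changes in site-level values, 12.4 fits that description, and analysing longitudinal change is a recognised choice. Adjusted in Section 3 may then be loose wording for taking baseline into account. This stands in part: it shows that the protocol is divided. It does not remove the conflict. CAL is defined as change and adjusted as well, and PD ≥5 mm is tied to a covariate that no model contains.

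The SAP, listed as a supplement but not seen here, may add baseline covariates. But the protocol itself fixes the model terms, so this is a conflict in stated text and not a detail left open. The subgroup models in 12.4 do bring in baseline characteristics such as age, stage and grade, but no baseline outcome value.

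A reader might infer that the primary estimate is biased or that the trial is underpowered. Neither follows. Under randomisation both analyses of PD and CAL are unbiased for the same mean difference, and the 90% was simulated with the 12.4 model.

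A reader might also infer that the free arm term is the whole cause, and that deleting it recovers 10 to 25% of the sample size. The last table shows otherwise.

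**Conclusion.** The inconsistency between Section 3 and 12.4 is real for PD, CAL, BoP and residual PD ≥5 mm, and should be resolved before unblinding. It does not extend to OHIP-5 or remission, for which Section 3 promises no adjustment.

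The efficiency cost has a known direction but an unknown size. For PD and CAL, adjustment loses nothing in large samples. It would be worth 10 to 25% of the variance (22 to 55 of 220 per arm) if r lies between 0.5 and 0.8 and the variances are equal. It is worth nothing if change is unrelated to baseline, and the simulation in 12.2 can be read that way, since changes are drawn without any stated dependence on baseline PD. The 10 to 25% is therefore a scenario and not an established loss.

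The variance formula does not carry over to the logit models. There, adding a covariate also changes the conditional odds ratio being reported.

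**What to change.** Rewrite the model paragraph in 12.4:

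- **PD:** outcome is the 6-week and 12-month values. Fixed effects are the baseline site value, the participant mean baseline value, visit, arm and arm-by-visit. Test the arm difference at each visit.
- **CAL and BoP:** same form, each with its own baseline values.
- **Residual PD ≥5 mm:** use baseline PD as the covariate, as 3.2 says. Section 12.4 calls this outcome tooth level and 3.2 calls it site level, so define the covariate at whichever unit is settled on.
- **OHIP-5:** optionally adjust for the baseline score.
- **Binary outcomes:** state that the odds ratio is conditional on the baseline covariates.

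A common baseline mean (no arm main effect, baseline kept as an outcome row) is an acceptable alternative only if a participant-by-visit covariance is added.

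The cost is a few lines of text. Sections 7.1 and 7.2 already collect all the baseline values. Section 12.2 should note that its simulation used the earlier model, or be re-run; the sample size need not rise on this account.
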